#### 87 **Objectives**

88 The ISESE project's main objective is to demonstrate that ingestion of *S. maxima*  
89 and a dosed physical activity program will decrease, both independently and  
90 synergistically, some CVD risks in overweight and obese subjects.

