#### 100 **Participants' eligibility**

101 The inclusion criteria will be the age between 18 and 45 years old of both sexes:  
102 40 overweight (Body mass index (BMI): 25-29.9 kg/m^2) and 40 obese (BMI: >30  
103 kg/m^2). The subjects' exclusion criteria will be: drinking more than 100 mL of  
104 alcohol a week, taking drugs and/or food or vitamin supplements, having a chronic  
105 disease, or having a physical or electrocardiographic injury that prevents them from  
106 engaging in any regular physical exercise. The elimination criteria will be that the  
107 program subjects' attendance will be lower than 80% and/or 20% change in their  
108 body weight during study.

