### 136 **Study design**

137 The study consists of *S. maxima* treatment during 14 weeks in a randomized,  
138 double-blind, placebo-controlled, and counterbalanced crossover design, aimed to  
139 eliminate inter-individual bias as well as boosting the reliability of final results;  
140 moreover, this design is commonly used in clinical trials in order to have better  
141 results and conclusions . Eligible participants (n= 80) will be divided into two  
142 groups, one with systematic practice of physical exercise (GEx) and other one  
143 without it (GNEx). The participants of each group will be randomized in equal  
144 proportions between *S. maxima* and placebo treatment, receiving either 4.5 g daily,  
145 in a non-transparent capsule during 12 weeks (6 weeks for the first treatment - 2  
146 weeks of washout period - 6 weeks for the second treatment) (Figure 1). Before  
147 any reported allergic reaction occurs, the treatment will be discontinued.

148 To maintain the overall quality and legitimacy of the clinical trial, code interruptions  
149 should occur only in exceptional circumstances when knowledge of the actual  
150 treatment is essential for further management of the participant. Investigators are  
151 encouraged to discuss with a Medical Advisor if they believe that unblinding is  
152 necessary. Unblinding should not necessarily be a reason for study  
153 discontinuation.

154 A student outside the research team will feed data into the computer in separate  
155 datasheets, so that the researchers can analyze the data without having access to  
156 information about the allocation treatments, storing all the participants' files in  
157 numerical order in a safe and accessible place. The participants' files will be stored  
158 for a period of five years after the end of the study.

159 The sample size was determined by using the statistical program G\*Power ,  
160 selecting a sample of 73 subjects with  $\alpha = 0.05$  and  $p = 0.85$ . This sample will be  
161 fixed to 80 subjects in order to anticipate the possible desertions from the study.

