## 162 **Maximum intensity tests**

163 Each subject will participate in four stress tests performed at maximum intensity  
164 (MIT) during the study; during MIT record, consumed O2 and produced CO2 will be  
165 taken by a gas analyzer (Cortex MetaLyzer® 3B, Germany), HR with a Polar H7  
166 sensor (Polar Electro, Lake Success, NY), and lactate in capillary blood samples  
167 will be assayed in a YSI 1500 Sport Lactate Analyzer (YSI Life sciences, OH,  
168 USA). The MIT protocol consists of using a cycle ergometer (Monark ergomedic  
169 828 E; Monark exercise AB, 105 Vansbro, Sweden) initiating with a workload of 50-  
170 75 W with increments of 15-30 W every 3 min for until 15 min or when the subject  
171 could no longer pedal more than 40 revolutions/min, finishing the test when  
172 reaching 90-100 % of the maximum HR reserve; MIT will not be valid for less than  
173 9 min (Figure 2). At the end of each increment load (3 min), capillary blood  
174 samples will be taken to determine lactate, and the physical perceived effort will be  
175 registered by using the Borg scale. Measurements of HR, glucose and blood  
176 pressure will serve to take care of the subject's health during each MIT.

177 Before the first MIT, subjects will decide to be in the GEx or GNEx, and then they  
178 will be divided randomly for the treatment, which consists in a daily dosage of 4.5 g  
179 of Spirulina or placebo in capsules which will be recommended the subjects to  
180 consume them before each meal every day during six weeks. The day after the  
181 first supplementation period, subjects will come back to perform the second MIT

182 with identical conditions to the first one. The third MIT will be performed after a  
183 washout period of two weeks to remove the effects of treatment and avoid any  
184 possible delayed effect of *S. maxima* in the organism. The last MIT will be  
185 performed after the second treatment with identical conditions to the previous three  
186 times. General fitness parameters will be measured the same day of all the MITs to  
187 have accurate results.

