### 188 **Randomization**

189 All subjects who consent to participation and who meet the inclusion criteria will be  
190 randomly assigned by an investigator who will not have any other interference in  
191 the clinical study; he will create a database with all the treatments through the  
192 duration of the study. Therefore, randomization will be carried out without any  
193 influence of the principal investigators. Participants will be randomly assigned to *S*  
194 *maxima* or placebo treatment with a 1:1 allocation according to a computer-  
195 generated random schedule stratified by site and the baseline score of the Action  
196 Arm Research Test using permuted blocks of random sizes with an online, central  
197 randomization service (TENALEA). Block sizes will not be disclosed, to ensure  
198 concealment.

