### 238 **Statistical analysis**

239 To evaluate data distribution, normality and homoscedasticity tests on each of  
240 response variables analyzed will be conducted. In order to analyze differences  
241 between variables before and after the study and between the groups, an ANOVA  
242 test will be performed. To analyze possible associations between variables, a  
243 bivariate correlation analysis will be used. To analyze independence between  
244 variables, a multiple regression analysis will be performed. The software to use is  
245 GraphPad Prism 6.

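### BMI class is fixed only for the whole trial while participants choose their exercise group, and the analysis names no BMI term for the exercise and synergy contrasts

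*Combined protocol and SAP*

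**What the plan says.** - **Participants' eligibility** sets the quota in total: "40 overweight (Body mass index (BMI): 25-29.9 kg/m 2 ) and 40 obese (BMI: >30" kg/m². No split by exercise group is given.
- **Study design** divides the 80 participants into two "groups, one with systematic practice of physical exercise (GEx) and other one" without it (GNEx). The text gives no size for either group. The equal allocation described there, "proportions between *S. maxima* and placebo treatment, receiving either 4.5 g daily", concerns the capsules within each exercise group.
- **Maximum intensity tests** makes exercise a personal choice: "Before the first MIT, subjects will decide to be in the GEx or GNEx, and then they" are randomised to a capsule.
- **Randomization** describes a "generated random schedule stratified by site and the baseline score of the Action" Arm Research Test. Neither factor is BMI class or exercise group.
- **Objectives** commits the trial to showing that Spirulina and physical activity reduce, independently and "synergistically, some CVD risks in overweight and obese subjects".
- **Statistical analysis** plans, for differences "between variables before and after the study and between the groups, an ANOVA", and adds for independence between "variables, a multiple regression analysis will be performed. The software to use is" GraphPad Prism 6. No covariate is named for either model.

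**The concern.** The main objective needs two contrasts besides the Spirulina effect. The exercise effect compares GEx with GNEx. Synergy is the difference between GEx and GNEx in the within-person Spirulina effect. Both compare different people, who sorted themselves into groups.

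BMI could plausibly influence who volunteers for an exercise programme five days a week. If the groups then differ in BMI class, a difference between overweight and obese people can be read as an effect of exercise or as synergy. The trial already treats BMI class as important enough for a recruitment quota, but that quota does not protect these contrasts and no stated model term does so.

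**Working it through.** **1. The plan's own figure.** Study design gives 73 subjects at alpha 0.05 and 0.85 (written as p, read here as power), raised to 80. No effect size, standard deviation, test or contrast is stated, so 73 cannot be reproduced. Back-solving with a two-sided test gives a standardised effect of 0.355 for a paired design or 0.711 for two groups of 36 and 37. The intended design cannot be identified, and 73 is not shown to be wrong. Only the total of 80, the 40/40 BMI quota and alpha 0.05 are used below. Everything else is an assumption.

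**2. Which contrasts are exposed.** For each person let D be the response on Spirulina minus the response on placebo, and M the mean lipid change over the two treatment periods. Let Z = 1 in GEx and B = 1 if obese.

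- Spirulina main effect: each person is their own control and capsule order is randomised, so unequal BMI mix between exercise groups does not bias it.
- Synergy: if D = a + s·Z + g·B, the unadjusted difference GEx − GNEx estimates s + (obese share in GEx − obese share in GNEx)·g.
- Exercise: if M = c + e·Z + h·B, the unadjusted difference estimates e + (the same gap)·h.

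So synergy is biased only if g is not zero (BMI class modifies the Spirulina effect), and exercise only if h is not zero (BMI class predicts lipid change).

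**3. Share carried over, and cost of adjustment.** Assume 40 per exercise group, with k overweight in GEx. The obese shares are (40 − k)/40 in GEx and k/40 in GNEx. The absolute gap is phi = (2k − 40)/40, which here is also the correlation between BMI class and exercise. Adjusting for BMI class multiplies the variance by 1/(1 − phi²).

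| Overweight/obese in GEx | phi | Variance factor after adjustment |
|---|---|---|
| 20/20 | 0 | 1.00 |
| 24/16 | 8/40 = 0.20 | 1/0.96 = 1.04 |
| 28/12 | 16/40 = 0.40 | 1/0.84 = 1.19 |
| 30/10 | 20/40 = 0.50 | 1/0.75 = 1.33 |
| 32/8 | 24/40 = 0.60 | 1/0.64 = 1.56 |
| 35/5 | 30/40 = 0.75 | 1/0.4375 = 2.29 |
| 40/0 | 1 | cannot be separated |

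For scale, take as reference the effect with 85% power at 40 per group and two-sided 0.05 (0.678 SD; this is a yardstick, not a figure from the plan). Adjusted power is then 83.5% at 24/16, 78.2% at 28/12 and 66.3% at 32/8.

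**4. If nothing is adjusted.** Let the BMI-class difference be 0.2, 0.5 or 0.8 SD of the analysed response, with no true effect. Bias = phi × difference, and the noncentrality is bias/√(1/40 + 1/40). At 28/12 and 0.5 SD, the bias is 0.4 × 0.5 = 0.20 SD and the noncentrality is 0.20/0.2236 = 0.89. The two-sided type I error is:

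| Overweight/obese in GEx | 0.2 SD | 0.5 SD | 0.8 SD |
|---|---|---|---|
| 24/16 | 5.4% | 7.3% | 10.9% |
| 28/12 | 6.4% | 14.3% | 29.3% |
| 32/8 | 8.3% | 26.3% | 56.4% |

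**5. How likely is a gap?** If choice were unrelated to BMI, a gap of 20 percentage points or more would arise by chance 11.7% of the time, and one of 40 points or more 0.07% of the time (hypergeometric, 40 per group). A large gap would therefore come from self-selection. The plan permits that but gives no indication of its strength.

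**6. Group size.** Unequal exercise groups cost precision and do not by themselves cause bias. The variance ratio is (1/a + 1/b)/(1/40 + 1/40): 1.07 at 50:30 and 1.33 at 60:20.

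**The case against.** **The root problem is self-chosen exercise.** BMI class is one trait among several that may follow the choice, along with motivation and fitness. This stands. Handling BMI class leaves both contrasts non-randomised.

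**The bias rests on effects that the documents do not report.** This also stands. The Discussion calls the link between body fat and lipid disturbances well known, and a reader might infer that synergy is therefore distorted. It does not follow. An association with lipid level cancels in each person's Spirulina-minus-placebo difference, and the primary outcome is change. What matters is whether BMI class predicts change or modifies the Spirulina effect.

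**Adjustment is available.** A reader might infer that only a recruitment rule can prevent the problem. The arithmetic contradicts this: adjustment works at every split short of complete alignment, and randomising exercise would also prevent systematic alignment. Body mass and height are measured at baseline, and the planned multiple regression could carry BMI. However, it names no covariates, so the plan does not commit to this.

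**Mild imbalance costs little.** True: at 24/16 the loss is about 1.5 points of power, and the type I error stays near 5% unless the BMI-class difference is large.

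**Group sizes may be stated elsewhere.** Figure 1 was not visible in the text reviewed, so sizes given only there cannot be excluded. The text gives none.

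**Conclusion.** The point holds as a conditional weakness with an inexpensive remedy. BMI class can differ between GEx and GNEx, and no stated analysis term accounts for it. With 40 per group, between 0.2 (24/16) and 0.75 (35/5) of any relevant BMI-class difference enters the exercise or synergy contrast. Adjustment removes this for 1.04- to 2.29-fold variance. That assumes the BMI-class effect is the same in both exercise groups and that class and exercise do not coincide.

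The documents do not show that imbalance will occur, how strong it would be, or that BMI class changes the response to Spirulina or exercise. They also give no ground for doubting the Spirulina-versus-placebo comparison on this account.

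**What to change.** **Main change, Statistical analysis.** State that the exercise and synergy contrasts will be estimated from a model containing exercise group, capsule and their interaction, with BMI class and BMI class by capsule as pre-specified terms. Confirm that the named software can fit it. This needs no new data, because BMI class is established at entry. The price is the variance factor shown above, which is negligible when the groups are similar.

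**Secondary change, Participants' eligibility and Maximum intensity tests.** Aim for about 20 overweight and 20 obese in each of GEx and GNEx, and monitor the four cells during recruitment. Keep this a soft target, because the cost of a hard quota grows with the alignment it is meant to prevent:

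- At a 24/16 pattern, 16/40 = 40% of obese volunteers choose GEx. Filling 20 places takes about 20/0.40 = 50 obese volunteers and, by symmetry, 50 overweight, or about 100 in all.
- At 30/10 the share is 25%: 20/0.25 = 80 per class, about 160 in all.
- At 35/5 it is 12.5%: 20/0.125 = 160 per class, about 320 in all.

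The model terms are needed even if the target is met, since removal for attendance below 80% can unbalance the cells later.

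**Reporting.** Describe the exercise and synergy contrasts as non-randomised. A reader might take balanced BMI cells as a cure for self-selection, but they do nothing for motivation, fitness or other traits. State the exercise-group sizes in the text, including any that Figure 1 shows.

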#### 109 **Call to participation, ethics and safety procedures**

110 University students of Ciudad Juarez, Mexico with overweight and obesity will be  
111 personally invited to participate. Participants will be informed of the purpose of the  
112 study, and of the physical, clinical and biochemical procedures, benefits, physical  
113 intensity tests, and risks, all before beginning the clinical trial. To guarantee the

114 good physical and mental health of the participants at the beginning of all the  
115 studies, a medical clinical laboratory study examination and an electrocardiography  
116 at rest tests will be performed. Noting that investigators are trained in  
117 cardiopulmonary reanimation and that the laboratory has the necessary  
118 communication tools and channels to perform emergency procedures. This study  
119 and all the procedures have been registered appropriately in ClinicalTrials.gov  
120 database (NCT02837666) and approved by the Bioethics Committee of the  
121 Universidad Autonoma de Ciudad Juarez (Supplementary files). That participants'  
122 acceptance formalized by means of written informed consent and their anonymity  
123 and confidentiality will be strictly enforced. This study will be conducted in  
124 compliance with the principles of the Declaration of Helsinki.

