### 199 **Adherence assessments**

200 Multiple methods will be used to assess treatment adherence including pill  
201 counting; reasons for non-compliance, and use of the capsules. Participants will  
202 return each week to receive new capsules. All treatment data will be recorded on  
203 the appropriate case report form.

204 **Dietary analysis**

205 All participants will be subjected to a nutritional survey to define the daily calories  
206 required to establish a custom diet. Dietary intake will be monitored through  
207 retrospective methods including the 24 h recall (which investigates intake over a  
208 specific day), and the food frequency questionnaire (a summary of usual intake of  
209 different categories of foods). These accurate and validated techniques allow  
210 quantifying the types and quantities of foods and beverages consumed during the  
211 period of interest in the past. Dietary intake evaluations will be performed at each  
212 MIT of the study in order to record the possible variability in food consumption  
213 patterns.

214 **Physical exercise protocol**

215 General health assessment and physical activity questionnaires (PAR-Q and YOU)  
216 will be conducted; this will be done to ensure that there are no physical  
217 impediments to exercise. GEx participants are going to exercise five days a week  
218 with the following protocol: between 5 and 10 min of warm-up exercise, between  
219 20-30 min muscular endurance exercise and 20-30 minutes of aerobic exercise  
220 (cardiovascular exercise): walking, jogging, running and/or cycling. Three days a  
221 week aerobic intensities will be between 60% and 80% and two days between 70%  
222 and 90% of the maximum HR reserve, and five final minutes of stretching.

223 **Sample collection and biochemical analysis**

224 Blood samples (8 mL) will be collected before and after each MIT from the  
225 antecubital vein into ethylenediaminetetraacetic acid (EDTA) tubes after 10-12 h of

226 fasting, plasma from blood samples will be obtained by refrigerated centrifugation  
227 (4°C) at 5 000 g for 10 minutes. Plasma glucose TC, HDL-c, LDL-c, and TAG  
228 concentrations will be analyzed by using standard enzymatic procedures (Jas  
229 Diagnostics, Inc. Mexico) with a spectrophotometer (Genesys 10 UV; Thermo  
230 Electron Corporation, USA). Plasma will be used to measure MDA and GSH  

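### Known allergy to the study product is not an exclusion, although the plan foresees allergic reaction and its crossover plans Spirulina for every participant who completes both periods

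*Combined protocol and SAP*

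**What the plan says.** The exclusions are given in one sentence under Participants' eligibility. After the alcohol limit it runs "alcohol a week, taking drugs and/or food or vitamin supplements, having a chronic" and continues "disease, or having a physical or electrocardiographic injury that prevents them from" exercising regularly. The elimination criteria that follow concern attendance and weight: "program subjects' attendance will be lower than 80% and/or 20% change in their" body weight. Neither list mentions allergy or intolerance.

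The Study design section describes a "double-blind, placebo-controlled, and counterbalanced crossover design, aimed to" reduce bias between individuals. Capsules are given "in a non-transparent capsule during 12 weeks (6 weeks for the first treatment - 2" weeks of washout, then 6 weeks of the second treatment). The same section says of the product that if "any reported allergic reaction occurs, the treatment will be discontinued", although the word that opens that sentence puts the stop before the reaction rather than after it.

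Three other places bear on entry. Call to participation, ethics and safety procedures provides, at the start, "studies, a medical clinical laboratory study examination and an electrocardiography" at rest. The Physical exercise protocol adds "General health assessment and physical activity questionnaires (PAR-Q and YOU"), with the stated aim of ruling out physical impediments to exercise. The Randomization section then assigns everyone who consents and meets the inclusion criteria.

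**The concern.** Allergic reaction is the only product-related harm that the plan names, and the plan deals with it only after exposure has begun. Nothing in the eligibility text keeps out a person who already knows that they react to the product.

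The design makes this matter more than it would in a parallel-group trial, because each participant is meant to take Spirulina in one of the two periods. The participants are otherwise healthy volunteers, and the Discussion describes the focus as prevention. A harm that the plan itself foresees, and that one question at entry could partly avert, should be reflected in who is let in. What is at stake is participant safety; the analysis is affected only incidentally.

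**Working it through.** The plan states no figure on this point, so the check is mainly a comparison of sections.

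**1. Is the harm foreseen?** Yes. Study design gives allergic reaction as a ground for discontinuing. The sentence is badly worded, but it shows that the authors had the event in mind.

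**2. Who is planned to receive Spirulina?** Each of the two sequences (Spirulina then placebo, placebo then Spirulina) contains one 6-week Spirulina period.
- Crossover: 80 × 1 = 80 of 80 participants are assigned Spirulina at some point.
- For comparison, a 1:1 parallel design of the same size: 80 × 1/2 = 40 of 80.
- Exception: a placebo-first participant who leaves before the second period is never exposed.

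**3. Does any entry step catch known allergy?**

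| Step | Section | What it covers | Allergy to the product? |
|---|---|---|---|
| Exclusion criteria | Participants' eligibility | Alcohol, drugs or supplements, chronic disease, physical or ECG problem preventing exercise | Not listed |
| Elimination criteria | Participants' eligibility | Attendance, weight change | Not listed |
| Medical and laboratory examination, resting ECG | Call to participation, ethics and safety procedures | General health; content not itemised | Not stated |
| Health assessment and activity questionnaires | Physical exercise protocol | Fitness to exercise | Not stated |
| Entry to randomisation | Randomization | Consent plus inclusion criteria | Not stated |

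**4. Test case.** Take a healthy student inside the age and BMI limits who once reacted to Spirulina and has not taken it since. The student takes no supplement now, has no clear chronic disease, can exercise and has a normal ECG. No exclusion applies, so the student is eligible as the text stands. If the student mentioned the reaction at the examination, the eligibility section would still give the screener no ground for exclusion.

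**5. Size.** The documents give no frequency of allergy to Spirulina or to any ingredient, and they do not describe the capsule shell or the placebo contents. The expected number of affected volunteers therefore cannot be derived. On power, the plan allows for 80 − 73 = 7 losses, or 7/80 = 8.75% of those enrolled. Each participant stopped for a reaction could use one of those 7 places, but nothing in the documents indicates that the allowance would be used up in this way.

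**The case against.** The best reply is that the plan already has several layers that would catch most such people.

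- **Consent.** Participants are told the procedures and risks beforehand and agree in writing. A person who knows of an allergy to Spirulina needs no unblinding to decline, because a crossover means that one of the periods contains it. This stands: self-exclusion would lower the real risk. It does not make the person ineligible, however, and the available text does not say that allergy is among the risks described.
- **The medical examination.** Its content is not itemised, and a clinician may well ask about allergies. That is possible, but the plan does not say so.
- **Chronic disease.** Some allergic conditions might count. A past reaction to one product in an otherwise healthy person does not clearly do so, and two screeners could reasonably differ.
- **The supplement exclusion.** It concerns current use. Someone who reacted and stopped passes it.
- **Safeguards during treatment.** Weekly capsule visits, trained investigators, emergency channels, discontinuation for allergic reaction and provision for breaking the code are all described. These limit harm once it occurs; they do not bear on who is enrolled.
- **Text not available.** The consent pages, a short stretch between Funding and Acknowledgements, and the supplementary files that the ethics section mentions could not be read. A warning or question could sit in the consent form. The eligibility section itself appears complete.

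What stands is that the practical risk is smaller than the eligibility text alone suggests. The omission from the exclusion list remains.

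**Conclusion.** The point holds as a gap in eligibility. The plan foresees allergic reaction, plans Spirulina for every participant who completes both periods, and leaves known allergy to the study product out of its exclusions. No entry question about it appears in the available text. The change is worth making for participant safety, and the trial remains interpretable without it.

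A reader might infer more than the documents support:

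- *A probability that an allergic person is enrolled.* This would need an allergy rate, which the documents do not give, and would assume that people who know they are allergic consent as readily as others. The result would only restate the assumption.
- *Losses confined to Spirulina periods.* That could hold for allergy to Spirulina itself. A reaction to a shared capsule ingredient could occur in either period, and one to a placebo ingredient would occur in placebo periods. The contents are not described, so no direction of loss can be claimed.
- *A threat to power.* None is shown against the allowance of 7.
- *An exclusion extended to other algae or cyanobacteria.* Nothing in the documents on cross-reactivity supports that.
- *A firm ceiling on volunteers turned away.* Probably very few would be, but without a rate no upper limit can be stated.

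The conclusion rests on the exclusion list being complete as printed, and on the unavailable pages not containing an allergy criterion.

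**What to change.** Reconcile Participants' eligibility with Study design by adding one exclusion: known allergy to the study products, meaning Spirulina or the contents of the placebo or capsule. Ask about it at the medical examination already planned under Call to participation, ethics and safety procedures, before randomisation, and record the answer. The screener will need the ingredient list for both capsules, which the plan does not give. If the consent form already carries such a question or warning, the protocol should say so and match it.

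The sponsor should also reword the discontinuation sentence in Study design, which cannot be applied as written. What that rule should be is for the sponsor, and none is proposed here.

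The cost is one line in the criteria, one question at an existing visit and probably very few volunteers turned away. Dose, schedule, randomisation and analysis are unchanged.

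### Habitual activity is neither limited nor recorded, and the non-exercise group is not asked to keep its usual activity, which can weaken the exercise and synergy contrasts

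*Combined protocol and SAP*

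**What the plan says.** - **Objectives.** The aim covers Spirulina "and a dosed physical activity program will decrease, both independently and" synergistically, so the effect of exercise and its interaction with Spirulina are both part of the main objective.
- **Study design.** Participants are split into two "groups, one with systematic practice of physical exercise (GEx) and other one" "without it (GNEx). The participants of each group will be randomized in equal" proportions to Spirulina or placebo. GNEx has no description beyond the absence of systematic exercise.
- **Maximum intensity tests.** Participants choose the exercise group themselves: "Before the first MIT, subjects will decide to be in the GEx or GNEx, and then they" are randomised to the capsules.
- **Participants' eligibility.** The one exclusion that touches exercise is for "having a physical or electrocardiographic injury that prevents them from" "engaging in any regular physical exercise. The elimination criteria will be that the", where the text passes into the elimination rules. Those rules are "program subjects' attendance will be lower than 80% and/or 20% change in their" body weight. Neither list mentions training already under way or taken up outside the programme.
- **Physical exercise protocol.** A health assessment and the PAR-Q and YOU questionnaires "will be conducted; this will be done to ensure that there are no physical" impediments to exercise. The plan gives the answers no other use.
- **Dietary analysis.** Diet is re-assessed at each MIT. No matching assessment of physical activity is described.
- **Outcome measures.** The primary outcome is change in the lipid profile after six weeks of treatment. The secondary outcomes are changes in fitness and redox status.
- **Statistical analysis.** ANOVA, correlation and multiple regression are named. No adjustment for baseline activity or fitness is specified.

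**The concern.** The GEx–GNEx comparison measures the effect of the programme only if GEx members receive exercise that is new to them and GNEx members do not take up training of their own. The plan secures neither condition and collects no activity data that would show whether they held.

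Two routes weaken the contrast. A GEx participant who was already training may gain less from the programme than an untrained one. A GNEx participant who starts training during the 14 weeks acquires part of the effect that the group is meant to lack. Either can reduce the estimated exercise effect on lipids, VO2 max and body fat, and the estimated difference in Spirulina effect between the two groups. Randomising exercise would not remove either route. Self-selection adds the possibility that trained people cluster in one group.

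**Working it through.** **Plan's own figures.** The plan gives no figure for prior training or for training taken up in GNEx, so there is nothing to reproduce on this point. Its sample size (73, raised to 80, with α = 0.05 and what appears to be power 0.85) cannot be tied to the exercise contrast, because no effect size, SD or test is stated.

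**Exercise contrast.** Let Δ be the mean change that the programme adds in a previously untrained person, on top of any change common to both groups.

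- GEx: a fraction a is already trained and, at worst, gains nothing. The mean added change is (1 − a)Δ.
- GNEx: a fraction b starts comparable training during the study. The mean added change is bΔ.
- GNEx members who train steadily before and during the study add no training-induced change. They do not enter the formula.
- Observed contrast = (1 − a)Δ − bΔ = (1 − a − b)Δ.

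If trained GEx members gain a share r of Δ instead of nothing, the factor becomes 1 − a(1 − r) − b.

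| Assumed a | Assumed b | Worst case, r = 0 | r = 0.5 |
|---|---|---|---|
| 0.20 | 0.10 | 1 − 0.20 − 0.10 = 0.70 | 1 − 0.10 − 0.10 = 0.80 |
| 0.30 | 0.20 | 1 − 0.30 − 0.20 = 0.50 | 1 − 0.15 − 0.20 = 0.65 |

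**Synergy contrast.** Let s be the Spirulina effect without added exercise and s + i the effect with it. Assume that newly added exercise is what modifies the effect. In the worst case the Spirulina effect averages s + (1 − a)i in GEx and s + bi in GNEx. The difference is (1 − a − b)i, so the same factor applies.

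**Spirulina versus placebo.** Each participant takes both, in randomised order. A stable training habit is present in both periods and cancels from the within-person difference.

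**What a loss could mean for power (illustration only).** Assume 40 participants in each exercise group, a two-sided test at 0.05, and a true standardised difference of 0.68, chosen because it gives 85% power at that size. With the noncentral t distribution:

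| Share of contrast lost | Power |
|---|---|
| 0% | 85.0% |
| 10% | 76.9% |
| 20% | 66.9% |
| 30% | 55.5% |
| 50% | 32.2% |

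Restoring power after a 30% loss needs about 1/0.70² = 2.04 times as many participants. The equal split is also an assumption, since participants choose their exercise group.

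**The case against.** Several stronger readings are tempting, and the documents do not support them.

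- **A reader might infer that trained people in GNEx dilute the contrast merely by being there.** The outcomes are changes, so a steady trainer in GNEx contributes no training-induced change. Only training taken up during the study counts. It is also uncertain that a regular trainer belongs in GNEx at all, because that group is described as being without systematic exercise. That description may mean only that GNEx does not follow the programme.
- **A reader might infer that trained GEx members receive nothing new.** The programme runs five days a week, combines muscular endurance with aerobic work, and scales aerobic intensity to each person's heart rate reserve. Zero gain is a worst case.
- **A reader might infer that the bias must run towards zero.** Participants choose their group. If steady trainers mostly choose GNEx, GEx is left with the people who have most to gain, and the contrast may be larger than a balanced mix would give.
- **A reader might infer that a null result would be uninterpretable.** Four MITs with gas exchange, heart rate and lactate give objective fitness data in both groups. The first could identify trained entrants, and a later rise in VO2 max in GNEx would suggest training outside the programme. This helps, but it does not replace an activity record, and the plan does not say that it will be used this way.
- **A reader might infer that the Spirulina result is compromised.** The randomised within-person comparison is largely protected.

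It is also fair to say that an entry restriction is partly a matter of preference. The protocol wants findings that extend to different populations, and recording activity with adjustment covers much of the same ground. Confounding from self-selection may well be the larger problem in this contrast. What survives all this is the gap in instruction, recording and analysis.

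**Conclusion.** The concern holds as a gap in conduct and recording that affects the exercise and synergy objectives. In the text available, habitual training is not limited or put on record as such at entry, GNEx is not asked to keep its usual activity, and outside activity is not followed during the study. The contrast is weakened mainly by trained GEx participants who gain less and by GNEx participants who begin training.

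The size cannot be found from the documents. Under assumed fractions of 0.20 and 0.10, the observed exercise effect would be 70% of the true one in the worst case, and 80% if trained participants gain half the usual benefit. If few participants train before or outside the programme, the loss is small. The formula describes dilution only. With self-selected groups, the net bias could run in either direction.

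The remedy is cheap and worth making.

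**What to change.** 1. **Study design and Physical exercise protocol:** ask GNEx participants to keep their usual physical activity for the 14 weeks.
2. **Physical exercise protocol:** record habitual activity in both groups at baseline. At each MIT, beside the dietary recall, record activity outside the programme in both groups. Report it by group and visit, so that training taken up in GNEx can be seen.
3. **Statistical analysis:** specify that the GEx–GNEx and Spirulina-by-exercise comparisons are adjusted for baseline activity or first-MIT VO2 max. Activity reported after baseline should be described rather than used as a covariate in the main model, because group membership may affect it. Adjustment will not remove all the confounding from self-selection, and the report should say so.
4. **Participants' eligibility (optional):** exclude people already in a regular exercise programme over a stated look-back period.

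The first three items cost one instruction, a short question at four existing visits and a sentence in the analysis section. They add no visit or assay and leave the exercise programme unchanged. If enrolment has begun, the instruction and the question can still be introduced for the remaining visits. The optional exclusion would slow recruitment somewhat, narrow the population, and still admit people who train informally.
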